Malnutrition is common among cancer patients, with prevalence rates ranging from 16–40% at diagnosis and increasing to 40–80% during treatment, depending on factors such as age, cancer type, and treatment modality(Bossi *et al*, 2021; Kaegi-Braun *et al*, 2021). Tumor location plays a crucial role, with the highest malnutrition rates observed in pancreatic (66.7%), esophageal/gastric (60.2%), head and neck (48.9%), and lung (45.3%) cancers(Hébuterne *et al*, 2014; Bossi *et al*, 2021).

Nutritional status in cancer patients is intricately linked to clinical outcomes. Tumor and therapeutic interventions notably impact nutritional health(Webb *et al*, 2020; Kipouros *et al*, 2023). Malnutrition significantly affects treatment tolerance, morbidity, survival, and quality of life(Hébuterne *et al*, 2014; Liu *et al*, 2021; Garutti *et al*, 2023). It can lead to reduced nutrient intake, cachexia, and impaired treatment efficacy(Muscaritoli *et al*, 2019; Holdoway *et al*, 2023). Early nutritional interventions have been shown to mitigate adverse clinical outcomes and reduce 30-day mortality in at-risk patients(Muscaritoli *et al*, 2019; Schuetz *et al*, 2019; Kipouros *et al*, 2023).

Although the association between malnutrition and adverse clinical outcomes has been well established (Muscaritoli *et al*, 2019; Liu *et al*, 2021; Kipouros *et al*, 2023), the benefits of nutritional improvement reported in different studies remain inconsistent (Schuetz *et al*, 2019; Kaegi-Braun *et al*, 2021). On the one hand, nutritional status might vary considerably over the course of treatment(Webb *et al*, 2020); on the other hand, psychological factors, sleep quality, and physical activity may further influence these outcomes (Nissim *et al*, 2024; Ye *et al*, 2024). High-quality and large-scale cohort studies that can capture dynamic changes in nutrition are needed to carry out more precise nutritional interventions or treatments to improve clinical outcomes. Hence, we established a cohort study to evaluate nutritional status and clinical outcomes in patients with common malignancies (NCOM study), aiming to provide evidence for personalized and precise nutritional treatment in oncology care.

53 **Methods**

54 **Study design**

55 The NCOM study is a multicenter, prospective cohort study designed to assess longitudinal
56 changes in nutritional status and their impact on clinical outcomes in cancer patients. We aim

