57 primarily to identify modifiable risk factors associated with malnutrition-related morbidity and
58 mortality and assess the effectiveness of targeted nutritional interventions. The secondary objectives
59 include examining variations in nutritional status across cancer types and treatment modalities and
60 exploring how nutritional health interacts with psychological well-being, sleep quality, and physical
61 activity. Participants diagnosed with common malignancies across multiple hospitals undergo
62 baseline nutritional assessments within 48 hours of admission, followed by structured follow-ups at
63 1, 2, 3, 6, and 12 months and then annually for an additional four years to track nutritional changes
64 and key clinical endpoints (Riboli, 2001). Nutritional status, the primary exposure factor, is
65 classified via validated screening tools and dietary intake assessments. Patients are stratified on the
66 basis of malnutrition severity, dietary intake, and nutritional support status, with classifications
67 updated at each follow-up, to evaluate their associations with short- and long-term outcomes (**Fig.**
68 **1**).

[figure not shown]

Fig. 1. The workflow of the NCOM study.

Study Setting & Population

Study sites

The NCOM study was conducted across 11 tertiary hospitals in Xi'an, Shaanxi Province, China.

The participating institutions included Shaanxi Provincial Cancer Hospital; the First Affiliated

Hospital of Xi'an Jiaotong University; the Second Affiliated Hospital of Xi'an Jiaotong University; Shaanxi Provincial People's Hospital; the First Affiliated Hospital of the Fourth Military Medical University; the Second Affiliated Hospital of the Fourth Military Medical University; Shaanxi Provincial Chest Hospital; and the Affiliated Hospital of Northwest University Xi'an No.3 Hospital; Xi'an International Medical Center Hospital; The First Affiliated Hospital of Xi'an Medical University; The Second Affiliated Hospital of Xi'an Medical University.

Recruitment strategy

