Eligible patients will be recruited by clinical medical staff. Recruitment will primarily occur through direct physician referrals during oncology consultations, supplemented by promotional materials in hospitals, such as posters, brochures, and electronic notices. Patients and their families who learn about the study through these materials can also self-refer by contacting the research team. The screening process consists of two steps. The first screening visit (SV1) is conducted remotely via online consultation or phone call to assess basic eligibility, including willingness to participate and key exclusion factors such as pregnancy or concurrent trial participation. Informed consent is obtained at this stage. Patients who pass SV1 will proceed to the second screening visit (SV2), which will be conducted onsite at each hospital. During SV2, medical records will be reviewed, and clinical assessments will be performed to confirm whether patients meet the inclusion and exclusion criteria. Only patients who meet all the criteria will be formally enrolled.

Inclusion criteria

- a. Age \geq 18 years.
- b. Histologically confirmed diagnosis of malignancy.
- c. Patients are scheduled to receive oncologic treatment, including surgery, chemotherapy, radiotherapy, or a combination.
- d. Mentally competent and able to provide informed consent.
- e. Willingness to participate in follow-up assessments
- f. Patients with multiple hospital admissions may be included in repeat assessments, with each admission counted as an independent case.

Exclusion criteria

Patients were excluded if they met any of the following criteria:

- a. Severe comorbidities that may interfere with participation (e.g., end-stage liver/kidney disease or severe cardiac failure).
- b. Patients with HIV/AIDS.
- c. Prior organ transplantation recipients.
- d. Expected survival of less than 6 months.
- e. Pregnant patients.
- f. Patients currently participating in another interventional clinical trial.

Sample size

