Upon enrollment, trained personnel will obtain informed consent and record demographic details, including sex, age, marital status, occupation, education, and socioeconomic status. Lifestyle factors such as smoking, alcohol, and tea consumption are documented, given their potential influence on nutritional status and cancer progression(Yuan *et al*, 2023). Medical history, including chronic conditions, previous diagnoses, medication use, and family history of malignancies, will also be recorded to assess genetic predispositions.

Cancer-specific data will be collected at baseline and updated at follow-ups to monitor disease progression and treatment response. This includes pathology-confirmed diagnosis, TNM staging at first diagnosis, and available molecular markers. The tumor burden will be reassessed at each visit, alongside major treatments (surgery, chemotherapy, radiotherapy, targeted therapy, and immunotherapy), with details on the type, duration, and response. Nutritional support, including enteral or parenteral nutrition in the preceding week, will be tracked to evaluate its impact on treatment outcomes.

Karnofsky Performance Status (KPS): The KPS evaluates a patient's ability to perform daily activities, the presence of physical discomfort, and overall performance status, providing a standardized measure of functional impairment(McNair *et al*, 2023).

Nutritional assessments

Nutritional assessments will be conducted via validated screening tools to evaluate nutritional status, risk factors, and dietary intake patterns. Two primary tools and standardized anthropometric

measurements will be employed to assess malnutrition risk and severity:

Subjective Global Assessment (mPG-SGA): The mPG-SGA scoring system consists of five sections: weight loss history, dietary intake changes, symptoms, activity and function levels, and age. Patients' nutritional status will be categorized on the basis of scores as normal (0–2 points), mild malnutrition (3–6 points), and moderate malnutrition (≥ 7 points)(Huo *et al*, 2023a). The version used in this study, mPG-SGAL11, is an adapted and validated version developed for Chinese cancer patients who that incorporates modifications on the basis of nationwide clinical feedback and statistical validation(Fu *et al*, 2022; Huo *et al*, 2023b).

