Nutrition support in and out of hospital Nutrition support	√	√	√	√	√	√	√
Laboratory biomarkers	√	√	√	√	√	√	√
EORTC QLQ-C30	√	√	√	√	√	√	√
HADS	√	√	√	√	√	√	√
PSQI	√	√	√	√	√	√	√
Leisure-time physical activity levels	√	√	√	√	√	√	√
KAP Questionnaire	√				√	√	√
Short-Term Clinical Outcome		√	√	√	√	√	√
Long-term clinical outcomes		√	√	√	√	√	√
Adverse Event Recording	√	√	√	√	√	√	√

299 **Table 1.** Follow-up schedule. SV: screening visit; KPS: Karnofsky Performance Status; mPG-SGA:
 300 Subjective Global Assessment; NRS-2002: Nutritional Risk Screening 2002; SDSAT: Simple Diet Self-
 301 Assessment Tool; EORTC QLQ-C30: European Organization for Research and Treatment of Cancer

Quality of Life Questionnaire C30; HADS: Hospital Anxiety and Depression Scale; PSQI: Pittsburgh Sleep Quality Index; KAP : Knowledge, Attitude, and Practice.

Statistical analysis plan

Baseline characteristics are summarized as the means \pm standard deviations (SDs) for normally distributed variables, medians with interquartile ranges (IQRs) for skewed data, and percentages for categorical variables. For group comparisons (e.g., normal vs. mild malnutrition vs. moderate malnutrition patients), independent t tests or Mann–Whitney U tests were used for continuous variables, and chi–square tests or Fisher’s exact tests were used for categorical data.

The primary outcome analysis will apply multivariate regression models, adjusting for age, sex, cancer stage, treatment modality, socioeconomic status, and baseline Karnofsky Performance Status (KPS). Logistic regression was used to assess binary outcomes (e.g., nutritional risk, survival), whereas linear regression was used to evaluate continuous variables (e.g., BMI changes, weight loss percentage). To account for repeated measures, generalized estimating equations (GEEs) model longitudinal variations in nutritional status, biomarkers, and quality of life.

For survival analysis, Kaplan–Meier curves were used to estimate overall survival (OS) and progression-free survival (PFS), with log-rank tests used to compare groups. Cox proportional hazards models were used to explore the associations between nutritional status and survival outcomes, incorporating time-dependent covariates where applicable.

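### The covariates named for the primary outcome analysis omit cancer type, although the protocol names it as a determinant of malnutrition, so the pooled association is left open to confounding by tumour site

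*Protocol*

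**What the plan says.** The Statistical analysis plan section of the protocol bases the primary outcome analysis on multivariable regression, "adjusting for age, sex, cancer stage, treatment modality, socioeconomic status, and baseline Karnofsky Performance Status (KPS"). The list is written as complete, with no wording that marks it as examples. The Cox models for survival follow in a separate paragraph and have no covariate list of their own.

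The Introduction describes malnutrition prevalence as "depending on factors such as age, cancer type, and treatment modality". It calls tumour location crucial and gives site-specific figures: "the highest malnutrition rates observed in pancreatic (66.7%), esophageal/gastric (60.2%), head and neck (48.9%), and lung (45.3%) cancers".

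The cohort is mixed. The Inclusion criteria require a "Histologically confirmed diagnosis of malignancy", with no restriction by site or to new diagnoses, and each readmission may count as a separate case. Under Demographics & Clinical Data, the diagnosis is recorded from pathology, the only stage variable named is "TNM staging at first diagnosis", and tumour burden is to be reassessed at each visit.

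Cancer type does appear later in the Statistical analysis plan section, as a subgroup factor. That part also plans interaction terms, and propensity score matching to balance the exposure groups at baseline, without listing the matching variables.

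**The concern.** The Introduction names three determinants of malnutrition. Two of them, age and treatment modality, are in the primary covariate list; the third, cancer type, is not. A confounder must be related to both exposure and outcome. The protocol itself supplies the first link. The second, that outcome differs between cancers, is not quantified in the protocol but is a natural possibility in a cohort open to any malignancy.

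If both links hold, part of a pooled malnutrition association would reflect which cancer the patient has. Such an association could appear even if nutritional status had no effect within any cancer. The pooled association is the study's main product, so its interpretation is at stake.

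**Working it through.** **1. Text comparison.**

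| Determinant of malnutrition named in the Introduction | In the primary covariate list? |
|---|---|
| Age | Yes |
| Treatment modality | Yes |
| Cancer type | No |

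**2. The planned effect, for scale.** The Sample size section gives each event rate twice, and the two versions disagree.

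- Rates in words, 20% unexposed and 24% exposed: OR = (0.24/0.76)/(0.20/0.80) = 0.316/0.250 = 1.26.
- Rates in brackets, 0.50 unexposed and 0.40 exposed: OR = (0.40/0.60)/(0.50/0.50) = 0.67, or 1.5 in size when inverted.

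The target of 1,538 reproduces from the bracketed rates. With two-sided alpha 0.05, 80% power, unpooled variance and 1:1 allocation (assumed), n per group = (1.960 + 0.842)² × (0.50×0.50 + 0.40×0.60)/0.10² = 384.6. The total is 769.2, and 769.2/(1 − 0.50) = 1,538.4. The worded rates need 3,366 before attrition (pooled formula), or 4,809 to 6,732 after 30% to 50% attrition. That contradiction is a separate matter. Here it means only that both 1.26 and 1.5 must be kept as benchmarks.

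**3. Crude two-cancer illustration.** From the protocol: malnutrition in 66.7% (pancreatic) and 45.3% (lung). Assumed: equal numbers, mortality m1 and m2, and no effect of malnutrition within either cancer.

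- Risk in the malnourished = (0.667·m1 + 0.453·m2)/1.120
- Risk in the others = (0.333·m1 + 0.547·m2)/0.880

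| m1 / m2 (assumed) | Malnourished | Others | Spurious OR |
|---|---|---|---|
| equal | equal | equal | 1.00 |
| 60% / 40% | 0.519 | 0.476 | 1.19 |
| 70% / 30% | 0.538 | 0.451 | 1.42 |
| 80% / 20% | 0.557 | 0.427 | 1.69 |

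**4. Sensitivity to the choice of cancers.** These are the two extremes of the four quoted rates. With head and neck (48.9%) against lung (45.3%) at 70%/30%, the risks are 0.4782/0.942 = 0.508 and 0.5218/1.058 = 0.493, and the OR is about 1.06.

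**5. Wider case mix, again with no effect within any site.**

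- *The four named sites in equal shares.* With assumed event rates of 30/26/20/24% (pancreatic, oesophageal/gastric, head and neck, lung), the spurious difference is 1.1 points (OR 1.06). With 60/40/20/35% it is 4.1 points (OR 1.19).
- *An assumed mix of 10/20/10/25% plus 35% other cancers, with 16% to 40% malnutrition in the others.* It is 1.5 to 3.3 points (OR 1.09 to 1.21) if the other cancers have a 17% event rate alongside the first set of rates. It is 5.4 to 11.9 points (OR 1.30 to 1.79) if they have 10% alongside the second set.

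The planned difference is 4 points (words) or 10 points (brackets).

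All results in steps 3 to 5 are crude. Adjustment for stage, treatment modality and KPS would absorb an unknown part of them.

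**The case against.** The strongest reply is that confounding has not been shown. The protocol gives no outcome rates by site, every mortality figure above is assumed, and all were chosen in the direction that raises the odds ratio. Step 4 shows how far the result depends on which cancers are paired. This stands: neither size nor direction can be derived, so a reader who infers that the main association is confounded goes further than the documents allow.

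A second reply is that propensity matching may include cancer type, since its variables are not listed, and that subgroups and interaction terms use it. It cannot be assumed that matching leaves cancer type out. But matching on unlisted variables does not put it into the named primary model, and subgroup results and interaction terms describe effect modification; they do not correct the pooled estimate.

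A third reply is that covariates may be left to a separate analysis plan. That would hold had the protocol been silent, but it names a list, and the list as written conflicts with its own Introduction.

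Two further inferences are tempting:

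- **Stage.** One might conclude that the model adjusts for stage at first diagnosis. The analysis section says only cancer stage, and the cancer-specific data are to be updated at follow-up. What stands is that no other stage variable is named and readmitted patients may have progressed.
- **Hospital.** One might call its absence a defect, since "The NCOM study was conducted across 11 tertiary hospitals". The protocol does not say that nutrition or outcome differs between them, and handling of centre is commonly left to the analysis plan.

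**Conclusion.** The point holds for cancer type. The named covariates leave out a determinant of malnutrition that the protocol itself identifies, in a cohort open to any malignancy, and nothing else in the plan repairs the pooled estimate. The estimate is open to confounding by site.

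In the two-cancer illustration the spurious odds ratio is 1.19 to 1.69, against a planned 1.26 or 1.5 in size. Two of the three scenarios exceed 1.26, and only the most extreme exceeds 1.5. These figures rest on assumed mortality, equal numbers and no other adjustment. They show that the bias could be as large as the effect sought, not that it will be. It vanishes if outcome does not vary by site.

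The stage variable is a secondary point of clarity. Hospital is optional.

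**What to change.** Add cancer type to the covariates of the primary regression models, with rare types grouped by a rule set in advance. List it among the propensity score variables. In the Cox models, adjust for it or stratify by it. Pathology-confirmed diagnosis is already collected, so the cost is a few degrees of freedom and the work of grouping rare cancers.

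In the same edit, state which stage variable enters the models, and consider the baseline tumour burden already assessed beside or in place of TNM at first diagnosis. Time since diagnosis could also help, but the protocol does not list it as collected. Adjustment for hospital may be considered but is not required by this point.

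The two sets of event rates in the Sample size section should be reconciled separately.

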Nutritional risk screening (NRS-2002): The NRS-2002 screening tool evaluates nutritional risk on the basis of three components: disease severity, nutritional status, and age. A total score of ≥ 3 indicates nutritional risk, warranting nutritional intervention, whereas a score of <3 requires weekly reassessment to monitor changes in nutritional status(Zhang *et al*, 2021).

Standardized anthropometric measurements: These measurements will include body mass index (BMI), percentage of weight loss, mid-arm circumference (MAC), triceps skinfold thickness (TSF), and handgrip strength. All measurements will be made under controlled conditions and repeated to ensure accuracy and reliability. To ensure methodological consistency, all measurements will be taken under fasting conditions, with patients wearing minimal clothing and no shoes.

Simple Diet Self-Assessment Tool (SDSAT): A validated self-reported dietary intake tool will be used to estimate the dietary intake of cancer patients. Compared with 24-hour dietary recall, the SDSAT has good reliability and validity(Jin *et al*, 2020).

Nutrition support in and out of the hospital: To evaluate the nutritional support of patients in and out of the hospital, patients need to provide information on the type of nutritional support (enteral or parenteral), formula, and supplemental dose.

Laboratory biomarkers

Biochemical markers will be analyzed to assess nutritional status, systemic inflammation, and metabolic function. Blood samples will be collected, processed, and stored following standardized protocols to ensure consistency among sites.

Serum ALB, prealbumin, and transferrin can be measured as indicators of protein-energy malnutrition, providing insights into nutritional depletion and muscle wasting risk. These factors

will be analyzed alongside C-reactive protein (CRP) to account for inflammation-related reductions in protein levels[30]. Inflammatory cytokines, including interleukin-6 (IL-6), interleukin-1 (IL-1), and tumor necrosis factor-alpha (TNF- α), serve as markers of systemic inflammation and metabolic dysregulation in patients with cancer-related malnutrition and cachexia(Keller, 2019).

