The nutritional knowledge section evaluates patients' understanding of nutrient composition, dietary recommendations, and the relationship between nutrition and cancer treatment outcomes. The attitude section measures patients' perceptions and beliefs regarding the importance of nutrition in managing cancer-related symptoms and treatment side effects. The practice section assesses

actual dietary behaviors, including food choices, meal frequency, and adherence to nutritional recommendations.

Short-Term & Long-Term Clinical Outcomes

Short-term clinical outcomes will focus on early posthospitalization events within 30 days of admission, providing insights into the immediate impact of nutritional status on patient recovery and complications. These outcomes will include 30-day survival status, intensive care unit (ICU) admissions, length of stay, and total hospitalization costs, with a specific breakdown of nutrition-related expenses, such as enteral and parenteral nutrition. Additionally, changes in body weight within 30 days of hospitalization will be monitored as a key indicator of early nutritional deterioration. The incidence of complications, including infections, malnutrition, and drug-related adverse effects, will be systematically recorded to assess treatment-related risks. These measures provide critical data on the role of nutritional status in influencing short-term recovery, treatment complications, and overall resource utilization.

Long-term clinical outcomes will be assessed through regular survival tracking at each scheduled follow-up visit. Patient survival status will be documented to analyze survival trends over time and the potential impact of nutritional interventions on overall prognosis. The follow-up evaluations will categorize patients as alive and disease-free, alive with disease progression, or deceased, with the cause of death recorded.

Adverse Event Recording

Adverse events (AEs) will be systematically recorded and monitored throughout the study to ensure patient safety and data integrity. AEs are defined as any unfavorable or unintended medical occurrence, regardless of their direct relationship with nutritional interventions or treatment. These may include treatment-related complications, gastrointestinal distress, metabolic imbalances, infections, allergic reactions, or other unexpected health changes.

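### The general linear-regression rule reaches length of stay and hospital cost with no provision for skew or unequal variance, and total cost contains the nutrition support tied to the exposure

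*Protocol*

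**What the plan says.** The protocol's Statistical analysis plan section sets the adjusted models by type of outcome: logistic regression for binary outcomes, while "linear regression was used to evaluate continuous variables (e.g., BMI changes, weight loss percentage"). The covariates are fixed as "adjusting for age, sex, cancer stage, treatment modality, socioeconomic status, and baseline Karnofsky Performance Status (KPS"). Skew is allowed for in two other places in that paragraph group: "medians with interquartile ranges (IQRs) for skewed data" in the baseline summaries, and "independent t tests or Mann–Whitney U tests were used for continuous variables" in unadjusted comparisons. Later in the section, propensity score matching is to balance baseline differences, and sensitivity analyses are to drop extreme values.

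The section on short-term and long-term clinical outcomes lists "length of stay, and total hospitalization costs, with a specific breakdown of nutrition-related expenses, such as enteral and parenteral nutrition" among the 30-day outcomes.

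Two passages tie nutrition support to the exposure. Under Nutritional assessments, an NRS-2002 score of 3 or more "indicates nutritional risk, warranting nutritional intervention". Under Study design, patients are stratified on the "basis of malnutrition severity, dietary intake, and nutritional support status".

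**The concern.** There are two separate issues.

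**Model.** Stay and cost are continuous, so the general rule sends them to linear regression on the raw scale unless something else is specified, and nothing else is. Outcomes of this kind are often right-skewed, with a spread that grows with the mean. In that case a raw-scale model can lose power. Constant-variance intervals can also be too narrow when the smaller group has the larger spread.

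**Cost as an outcome.** A patient at nutritional risk is one for whom support is warranted, and support is an item on the bill. When groups are formed by support status, the exposure is itself receipt of that item. The groups can then differ in total cost even if recovery is identical, and the difference could be misread as an effect of nutritional status on recovery.

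**Working it through.** **The plan's own figure.** The protocol gives no power figure for stay or cost. Its target of 1,538 rests on a binary event rate. It reproduces from the rates in symbols (0.50 and 0.40), two-sided 0.05, 80% power and 50% attrition:

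- per group: (1.960 + 0.842)² × (0.50×0.50 + 0.40×0.60) / 0.10² = 7.849 × 49 ≈ 384.6
- total: 2 × 384.6 / 0.5 ≈ 1,538

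The rates in words (20% and 24%) do not give this figure. That contradiction is a separate matter.

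**Which n applies.** The 30-50% attrition is stated for multiyear follow-up. Stay and cost are 30-day outcomes, so n = 1,538 is used.

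**Assumptions (not in the protocol).** Log-normal outcome with log SD s = 0.6, 0.8 or 1.0; 30% exposed (461 versus 1,077); ratio of means 1.2; no covariates.

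**Power, log scale.** SE = s × √(1/461 + 1/1077) = 0.0557 s; effect ln 1.2 = 0.1823; power = Φ(0.1823/SE − 1.96).

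**Power, raw scale.** Set the unexposed mean to 1, so the difference is 0.2, and let CV = √(exp(s²) − 1).

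- constant-variance SE = CV × √[(461×1.44 + 1077)/1538] × 0.0557 = 0.0592 CV
- true SE = CV × √(1.44/461 + 1/1077) = 0.0637 CV
- power = Φ[(0.2 − 1.96 × constant-variance SE) / true SE]

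| s | CV | linear, formula | log scale, formula | linear vs log, simulation |
|---|---|---|---|---|
| 0.6 | 0.658 | 99.8% | 99.98% | 99.9% vs 100% |
| 0.8 | 0.947 | 93.3% | 98.4% | 94% vs 98% |
| 1.0 | 1.311 | 71.7% | 90.6% | 72% vs 90% |

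Formula and simulation agree. A simulated log-link model with robust standard errors gives about 94% (s = 0.8) and 72% (s = 1.0), the same as linear regression.

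**Interval coverage.** Let r be the ratio of means, with SD proportional to the mean and 30% exposed. In units of the unexposed variance divided by n:

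- true variance of the difference: r²/0.3 + 1/0.7
- variance assumed by the model: (0.3r² + 0.7)(1/0.3 + 1/0.7)
- r = 1.2: 5.390/6.229 = 0.865; coverage = 2Φ(1.96√0.865) − 1 ≈ 93.2%
- r = 1.5: 6.548/8.929 = 0.733; coverage ≈ 90.7%

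Simulation gives about 92-93% and 90-91%. With equal groups the two variances coincide and coverage is about 95%. Robust standard errors bring the 30% case back to 94-95%. With no true difference, the rejection rate stayed between 0.043 and 0.054 at n = 1,538.

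**Built-in cost difference.** Proportional rise in mean cost = (support cost as a share of the stay's cost) × (difference in receipt between groups). Both inputs are assumed:

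- low: 0.02 × 0.30 = 0.6%
- middle: 0.05 × 0.50 = 2.5% to 0.10 × 0.50 = 5%
- high: 0.20 × 0.70 = 14%

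None of the listed covariates represents nutrition support. Matching on baseline cannot take a component out of the outcome. A larger sample estimates the built-in part more precisely but does not shrink it.

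**The case against.** The case on the other side is substantial, and much of it stands.

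- *The assignment is inferred.* The sentence gives BMI change and weight loss as examples and names neither stay nor cost. Linear regression does not forbid a log-transformed outcome, and a separate analysis plan may settle the scale. A reader might infer that the protocol expressly puts these outcomes on the raw scale; it does not. What remains is a general rule, stated in the protocol itself, with no adjusted alternative for skewed outcomes.
- *Skew is not ignored.* Medians, Mann-Whitney tests, distribution-dependent correlations and exclusion of extreme values all appear. None of these is an adjusted model for a skewed outcome, and for stay and cost the extreme values may be the admissions of most interest.
- *The power loss could be made to look larger.* A reader might halve the sample to 769 for 50% attrition. The protocol ties that attrition to multiyear follow-up, so it does not carry over to 30-day outcomes. Log-normal data also favour the log scale, and a ratio of geometric means is a different estimand from a difference in mean days.
- *A log-link model for cost does not recover power.* This stands. Robust standard errors are worth having for the intervals only.
- *Nutrition expense belongs in a resource-use total.* This also stands. The breakdown is already collected, so net cost can be computed. The NRS-2002 wording says support is warranted, not that it was given, and this is why the size of the built-in part is an assumption. That total cost contains support cost is not an assumption.

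**Conclusion.** The point holds in a limited form. By its general rule, the protocol leaves length of stay and cost to linear regression without provision for skew or unequal variance. Under assumed log-normal skew at n = 1,538, 30% exposed and ratio 1.2, the power cost is negligible at log SD 0.6, about 4 points at 0.8 and about 18 points at 1.0. The coverage shortfall (92-93% at ratio 1.2, 90-91% at ratio 1.5) needs both unequal groups and a real difference. It comes from unequal variance, not from linear regression as such. It would be wrong to conclude that the intervals fail generally or that false positives rise.

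The cost point needs no distributional assumption. Part of any association between nutritional status and total cost can arise from the support itself; the range of 0.6-14% rests entirely on assumed receipt and cost shares. No stated sample size or power figure is affected. Priority is low to moderate.

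**What to change.** Add to the protocol's Statistical analysis plan section:

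1. Length of stay is analysed on the log scale and reported as a ratio of geometric means.
2. Cost is analysed by a linear or log-link model with robust standard errors, to correct the intervals and not to gain power.
3. For the association of nutritional status with recovery, cost net of nutrition-related expenses is reported beside total cost. Total cost stays as the resource-use outcome.

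No new data are needed, because the nutrition-expense breakdown is already collected. The price is that stay effects are expressed as ratios and not days, and that there is one extra cost analysis.
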